10.1.2 Reporting of (Serious) Adverse Events and other safety related events

Reporting to Sponsor

The following events are to be reported to the Sponsor within 24 hours upon becoming aware of the event:

- All SAEs
- Health hazards that require measures
- Device deficiencies

The Sponsor will evaluate SAEs with regard to causality and seriousness. Device deficiencies are assessed regarding their potential to lead to an SAE.

Reporting to Authorities [ClinO Art. 42]:

In Category C studies it is the Investigator's responsibility to report **serious adverse events** in Switzerland which are

- related or possibly related to the medical device under investigation
- related or possibly related to study procedures

to the Ethics Committee via BASEC within 7 days. The Sponsor reports within the same timeline to Swissmedic (incl. events from abroad).

- **Health hazards** that require measures are reported via BASEC within 2 days [ClinO Art. 37].

Periodic safety reporting:

In Category C studies a yearly safety update-report is submitted by the Investigator to the Ethics Committee and by the Sponsor to Swissmedic.

10.1.3 Follow up of (Serious) Adverse Events

The adverse event shall be followed by the PI until its resolution or until the adverse event is recognized as permanent or stable condition by the PI. Follow-up investigations may be necessary according to the PI's medical judgement. In this situation, the follow-up does not have to be documented in the CRF but must be noted in the source documentation.

In case of SAE / SADE the sponsor can be contacted following the list below. If the first person in the list cannot be timely contacted, the PI should try to contact the next and so on.

Contact order

Contact order	Name	Mobile	Office	E-Mail
1	[name]	[contact]	Head of SIV	[contact]
2	[name]	[contact]	Senior Director	[contact]

Table1. Contact information of the sponsor in case of SAE/SADE

11. STATISTICAL METHODS

11.1 Hypothesis

The feedback canceller used in the IMD is an extension of the feedback canceller implemented in the RMD but newly designed for dynamic situations, e.g. insertion of the device, phone call, removal... Regarding feedback performances, we can expect less annoyance of feedback in some dynamic situations which are tested within the live feedback test. The feedback canceller in static situations is based on the same principle and functions the same in the IMD as in the RMD.

Variance in the results can come from manipulation, individual programmed gain, acoustical coupling within the ear canal, or individual rating. However, there are no technical reasons that feedback annoyance with IMD should be higher than with the RMD. Therefore, a one-sided test will be used to evaluate the benefit of the IMD in terms of feedback annoyance.

11.2 Determination of Sample Size

The primary outcome, the live feedback test, measures the feedback annoyance on a visual analogue scale for different manipulations that could produce feedback. An internal pilot test found an average improvement of 1.54 points (SD 1.63 points) with the newly developed feedback canceller (prototype) on the feedback annoyance scale. This effect was obtained on a group of listeners with moderate to severe hearing loss.

A test with a homogenous group of participants, i.e. hearing loss and hearing aid style, and repeated measures would require 11 subjects to show an effect with an alpha value of 2.5%, a power of 80%, and an effect size of 0.94. Similar conditions can be found in subjects who are eligible to be fitted with the Super Power BTE device. Therefore, 11 participants should be recruited for the third phase.

For the first and second phases, the inclusion criteria for the hearing loss degree covers a larger range of configurations. The IMD styles, i.e. miniRITE-T and miniRITE-T rechargeable, offer also more acoustical options than the SP style during the fitting. These 2 parameters, the hearing loss degree and acoustical coupling, are known to influence the risk of acoustical feedback. This added variation might reduce the effect size of the feedback annoyance with the IMD and must be compensated with an increased sample size. For the first and second phases, we propose to expand the sample size to 22 subjects to compensate for the effect size reduction. A power of 83% can be achieved with an effect size of 0.65, alpha value of 2.5% and 22 subjects.

11.3 Statistical criteria of termination of trial

There are no plans for early termination of the trial.

11.4 Planned Analyses

11.4.1 Datasets to be analysed, analysis populations

Primary analysis of the primary outcome will be based on the intention-to-treat (ITT). The ITT population will include all participants with associated primary outcome data, excluding only subjects who were deemed ineligible following the screening visit, those who withdrew from the trial and were unwilling for their previously collected data to be utilised or those who failed to provide baseline.

11.4.2 Primary Analysis

The live feedback test provides a measure of feedback annoyance on a visual analogue scale. A paired t-test will be used to evaluate if the observed difference (RMD - IMD) is higher than 0 in a first intention. However, the following factors are identified and should be included within a second analysis based on mixed-effect regression:

- Test device RMD vs IMD which is the main fixed effect,
- Participant as a random effect for the repeated measures, and the side (left-right) as nested random factor within participant,
- Feedback risk with the acoustical coupling, the hearing loss degree, and maximum gain measured from the REM,
- Manipulation as fixed effect.

The second analysis should provide more details about the dependencies between hearing loss degree, acoustical option and feedback annoyance.

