9.2 Assessments of outcomes

9.2.1 Assessment of primary outcome

The primary outcome is the live feedback testing results of the IMD compared with the RMD. The hearing aids will be programmed with the same gain and feedback elicited in simulated real-life situations that cause feedback including: Inserting and removing the hearing aids from the ears, holding a telephone up to the ear, sitting close to a wall, putting the hand up to the ear. The subjects will answer questions about the annoyance caused by the elicited feedback. The feedback test will be tested with the RMD and the IMD at the second appointment.

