11.4.4 Interim analyses

We plan to have 3 interim and one final analyses. A separate analysis will be performed after each completed phase. These interim analyses are based on a one-sided superiority hypothesis, i.e. there is less feedback annoyance with the IMD than with the RMD.

Valuable information may also be gained by summarizing the results of all the conducted comparisons at the end of the study. It should be presented in an identical form to allow direct comparison on the estimates and their confidence limits.

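### Fitted as listed, the supporting mixed model of the live feedback test gives confidence limits for the device effect that are too narrow if benefit differs substantially between participants

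*Protocol*

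**What the plan says.** Section 11.4.2 of the protocol plans two analyses of the live feedback test. The first is a paired t-test of whether the RMD minus IMD difference exceeds zero. The second is a mixed-effect regression whose factors are listed one by one:

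- device: "Test device RMD vs IMD which is the main fixed effect"
- random part: "Participant as a random effect for the repeated measures, and the side (left-right) as nested random factor within participant"
- feedback-risk covariates (coupling, hearing loss degree, maximum gain from the real-ear measurement)
- manipulation, as a fixed effect

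No interaction with device is listed, fixed or random. The section closes by giving the second analysis an explanatory purpose: to describe how annoyance depends on hearing loss degree and acoustical option.

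Section 9.2.1 gives the manipulations as "Inserting and removing the hearing aids from the ears, holding a telephone up to the ear, sitting close to a wall", followed by raising the hand to the ear. That is four, or five if insertion and removal are rated separately.

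Section 11.1 states "Variance in the results can come from manipulation, individual programmed gain, acoustical coupling within the ear canal, or individual rating". It expects less annoyance only in some dynamic situations, with static behaviour unchanged. Section 11.2 says of the wider range of hearing loss and coupling in Phases 1 and 2: "This added variation might reduce the effect size of the feedback annoyance with the IMD".

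Section 11.4.4 says of the results summarised over all comparisons: "It should be presented in an identical form to allow direct comparison on the estimates and their confidence limits". It does not say which of the two analyses supplies them.

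**The concern.** Random intercepts for participant and for side remove differences in the level of annoyance. They cancel out of the RMD minus IMD contrast and say nothing about whether the contrast itself differs between people. With several ratings per device from each participant, the listed model treats every rating as independent evidence on the device effect. Only 11 or 22 people supply such evidence.

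Differences in benefit are plausible. A participant with little feedback on either device has little to gain, and the protocol ties feedback risk to hearing loss degree and coupling, which vary between participants. Nobody needs to be worse on the IMD for this to happen.

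What is at stake is the device p-value and confidence limits of the second analysis. If those limits were used in the comparison of section 11.4.4, they could be too narrow, and by different amounts in different phases if benefit varies more in Phases 1 and 2.

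**Working it through.** **Plan's own figures.** Paired t-test, one-sided 2.5%, noncentral t with n - 1 df:

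- n = 11, effect size 0.94: power 80.2% (stated 80%)
- n = 22, effect size 0.65: power 82.8% (stated 83%)

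Both reproduce with the participant as the unit. The pilot ratio is 1.54 / 1.63 = 0.945.

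**Inputs.**

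- From section 11.2: V = 1.63² = 2.657, taken as the variance of participant mean differences; n = 11 or 22.
- Assumed: K = 4 or 5 manipulations; S = 1 or 2 sides rated; m = K × S = 4, 5, 8 or 10 ratings per device; p = share of V that is true variation in benefit. The documents do not give p, so 0 to 75% is shown.

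**Formulas (balanced data).**

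- Rating residual variance: σ² = (1 - p) V m / 2
- Correct SE² = V / n
- Residual df of the listed model: ν = 2nm - nS - 1 - (K - 1). This gives 73 to 193 for n = 11 and 150 to 391 for n = 22, against 10 and 21 at participant level.
- (model SE / correct SE)² = (1 - p) + p(n - 1)/ν + nSD/(mVν)

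Here D is the sum over manipulations of (benefit in that manipulation - mean benefit)². It is zero if benefit is the same everywhere. If benefit occurs only in some manipulations, the unmodelled device-by-manipulation difference enters the residual and partly offsets the fault.

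**Worked cases at p = 50%.**

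- n = 22, m = 10, equal benefit: √(0.5 + 0.5 × 21/391) = 0.726
- n = 11, m = 4, equal benefit: √(0.5 + 0.5 × 10/73) = 0.754
- n = 11, m = 4, benefit 3.08 in two of four manipulations (mean 1.54): D = 4 × 1.54² = 9.486; added term 11 × 9.486 / (4 × 2.657 × 73) = 0.1345; ratio √(0.5685 + 0.1345) = 0.838
- n = 22, m = 10, benefit 2.567 in three of five: D = 3 × 1.027² + 2 × 1.54² = 7.905; added term 22 × 2 × 7.905 / (10 × 2.657 × 391) = 0.0335; ratio √(0.5269 + 0.0335) = 0.749

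**Coverage of the nominal 95% interval** (simulation, ranges over n and m, rounded):

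| Share p | SE ratio, equal benefit | Coverage, equal benefit | Coverage, benefit in some manipulations |
|---|---|---|---|
| 0% | 1.00 | about 95% | 95-96% (slightly too wide) |
| 10% | 0.95-0.96 | about 94% | 94-96% |
| 25% | 0.87-0.89 | 91-92% | 92-95% |
| 50% | 0.72-0.76 | 85-87% | 86-90% |
| 75% | 0.54-0.60 | 71-76% | 73-84% |

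In the last column the smaller loss belongs to fewer ratings per device. The participant-level paired interval stays near 95% in these settings. REML fits of the listed model (n = 22, five manipulations, two sides, equal benefit, 300 runs each) gave 93.7 / 91.3 / 83.0 / 73.0% at 0 / 25 / 50 / 75%, in line with the balanced calculation.

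**In points.** The participant-level half-width is 2.228 × 1.63/√11 = 1.10 for n = 11 and 2.080 × 1.63/√22 = 0.72 for n = 22. At p = 50% with equal benefit, the listed model gives 0.70-0.74 and 0.50-0.52. Part of the gap is its larger df. With p = 0 and n = 11 it would give 0.97-0.98, and that would be correct.

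**The case against.** Several points on the other side have force.

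- *Model detail belongs in the statistical plan.* Section 11.4.2 lists factors rather than a formula, and its wording does not rule out a random device effect. The statistical plan is an appendix that is not shown and may add one. This stands in part. The protocol does name a specific random structure, and a plan that follows it literally carries the fault forward.
- *The second analysis is explanatory.* This stands, and it is the main reason for low severity. A reader might infer that the primary test or the sample size is unsound. The documents do not support that: both rest on the paired t-test, which is unaffected when run on one mean difference per participant.
- *The link to section 11.4.4 is only possible.* This stands. A reader might infer that the limits compared across phases come from the mixed model. The section does not say so.
- *Evidence for varying benefit is indirect.* Section 11.1 speaks of variance in results, not in benefit, and section 11.2 says only that the effect size might fall. The named sources are covariates, and interactions with device could absorb part of the variation, but none is listed. The share is therefore unknown.
- *Benefit only in some manipulations offsets the fault.* This stands and is included above. It reduces the loss of coverage without removing it at larger shares.

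One could also quote one-sided error rates of about 12 to 15% at a 75% share. That figure needs zero mean benefit with some participants worse on the IMD, whereas section 11.1 says "there are no technical reasons that feedback annoyance with IMD should be higher than with the RMD". It is not a fair measure of the risk here. The loss of coverage is: it remains when every participant's benefit is zero or more (84.3-86.8% at a 50% share with equal benefit across manipulations).

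**Conclusion.** The point holds conditionally and at low severity. If the second analysis is fitted with only the listed random effects, and benefit differs substantially between participants, its confidence limits for the device effect are too narrow. The loss is modest at a 25% share, clear at 50% and large at 75%. It is smaller where only some manipulations benefit and few ratings are taken per device, and negligible or absent at 10% or less. The shares, the number of ratings and balanced data are assumptions, so the actual size cannot be stated from the documents. The concern does not extend to the first-line test or the sample size.

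**What to change.** In section 11.4.2, add a by-participant random device effect to the live feedback model, with Satterthwaite or Kenward-Roger degrees of freedom. If benefit is expected only in some manipulations, also add device-by-manipulation as a fixed interaction. State that if the fit is singular, notably at n = 11, inference on the device effect comes only from the participant-level paired t-test and the mixed model is descriptive. In section 11.4.4, state that the estimates and confidence limits compared across phases come from the participant-level paired analysis or from the model with the added term.

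The cost is one or two model terms and a few sentences, with no change to data collection or sample size. The downside is somewhat wider intervals and possible convergence trouble in Phase 3, which the fallback covers.

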11.4.3 Secondary Analyses

Speech Test

Speech is measured with a standardized test called the WaKo Rhyme test from Wallenberg and Kollmeier (1989). The WAKO test is a closed word recognition test, i.e. one word is presented acoustically, and the subject must choose one answer out of five proposals. The outcome of each tested item is either 0 and 1 which can be modelled by a logistic mixed effect regression. Fixed effects are test condition, listening condition, hearing loss, i.e. 4- frequencies average of the best ear. Random effects are the participants and the tested item.

Product Questionnaire

Experienced acoustical feedback and sound quality are reported via a 5-points Likert scale. Differences between test conditions will be analysed with Wilcoxon signed-rank test.

11.4.4 Interim analyses

We plan to have 3 interim and one final analyses. A separate analysis will be performed after each completed phase. These interim analyses are based on a one-sided superiority hypothesis, i.e. there is less feedback annoyance with the IMD than with the RMD.

Valuable information may also be gained by summarizing the results of all the conducted comparisons at the end of the study. It should be presented in an identical form to allow direct comparison on the estimates and their confidence limits.

11.4.5 Safety analysis

The adverse event risks of taking part in the study have been assessed to be low. Numbers of adverse events and serious adverse events will be cross-tabulated for each IMD style and categorised by severity. No formal statistical analysis will be conducted, but AEs and SAEs will be closely monitored throughout the process.

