9.2.3.1 Adverse events

For the recording of adverse events the subjects will be asked for a description of the event including time/date of onset, how long it lasted, how many times it occurred, and if it caused discomfort or pain or a disruption of hearing ability. Before the end of each appointment, the subjects will be asked if they have experienced any adverse events. It will be explained that adverse events are not restricted to problems related to the hearing aids or their hearing but can include allergies, broken legs, headaches, etc. They will be recorded on the AE forms in the CRF.

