10.1 Medical Device Category C studies

Device deficiencies and all **adverse events (AE)** including all **serious adverse events (SAE)** are collected, fully investigated and documented in the source document and appropriate case report form (CRF) during the entire study period, i.e. from patient's informed consent until the last protocol-specific procedure, including a safety follow-up period [ISO 14155]. Documentation includes dates of event, treatment, resolution, assessment of seriousness and causal relationship to device and/or study procedure.

The information on AEs is systematically collected by the clinician at each study visit. They will follow the procedures outlined in SOP ID106_AE Reporting. The subjects are asked at each appointment if they have experienced any events since the last appointment. During the appointments the subjects are then asked questions about the event to gather details and to determine the severity of the event. If a subject reports pain that results in the inability to use the device, he will be withdrawn from the study in order to avoid any pain from using the device and to remove partial data from the study. For reports of pain caused by insertion or the dome itself, the problem can be addressed in the clinic. For example, a different style or size of dome can be placed on the hearing aid, and re-training of insertion can be performed with the subject to avoid wrong or forceful insertion of the device. For reported pain they will be advised to not wear the device for 24 hours before resuming use.

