10.1.1 Definition and Assessment of (Serious) Adverse Events and other safety related events

Adverse Event (AE)

Any untoward medical occurrence, unintended disease or injury or any untoward clinical signs (including an abnormal laboratory finding) in participants, users or other persons whether or not related to the investigational medical device [ISO 14155: 3.2].

This includes events related to the IMD or the RMD and to the procedures involved. For users or other persons this is restricted to events related to the investigational medical device.

Adverse Device Effect (ADE)

Adverse event related to the use of an investigational medical device [ISO 14155: 3.1].

This includes any adverse event resulting from insufficient or inadequate instructions for use, deployment, implantation, installation, operation, or any malfunction of the investigational medical device. This includes any event that is a result of a use error or intentional misuse.

AEs/ADEs include:

- Exacerbation of a pre-existing disease or condition.
- Increase in the frequency or intensity of a pre-existing episodic disease or medical condition.
- Any disease or medical condition detected or diagnosed after treatment with the study intervention device even though it may have been present yet undetected prior to the start of the clinical investigation.
- Any continuous persistent disease or symptoms present at baseline that worsen following the start of the clinical investigation.

- Events considered by the investigator to be related to any of the clinical investigation-mandated procedures.
- Abnormal assessments, e.g. physical examination findings, will be reported as AEs/ADEs if they represent a clinically significant finding that was not present at baseline or that has significantly worsened during the course of the clinical investigation.
- Test abnormalities will be reported as AEs/ADEs if they represent a clinically significant finding, symptomatic or not, which was not present at baseline or has significantly worsened during the course of the clinical investigation.

AEs/ADEs do not include:

- Pre-planned interventions or occurrences of endpoints specified in the CIP are not considered AEs/ADEs, if not defined otherwise.
- Unrelated medical or surgical procedures, e.g. surgery, endoscopy, tooth extraction, transfusion. However, the event leading to the procedure may be considered an AE. If this event is serious, the procedure will be described in the SAE/SADE narrative.

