- Any pre-existing disease or medical condition that remains stable and does not worsen during the course of study participation.
- Situations in which an adverse change did not occur, e.g., hospitalizations for unrelated cosmetic elective surgery or for social and/or convenience reasons.

Serious Adverse Event (SAE) [European regulation on medical devices 2017/745, art. 58].

Any adverse event that led to any of the following:

- (a) death,
- (b) serious deterioration in the health of the subject that resulted in any of the following:
 - (i) life-threatening illness or injury,
 - (ii) permanent impairment of a body structure or a body function,
 - (iii) hospitalisation or prolongation of patient hospitalisation,
 - (iv) medical or surgical intervention to prevent life-threatening illness or injury or permanent impairment to a body structure or a body function,
 - (v) chronic disease,
- (c) foetal distress, foetal death or a congenital physical or mental impairment or birth defect.

This includes device deficiencies that might have led to a serious adverse event if a) suitable action had not been taken or b) intervention had not been made or c) if circumstances had been less fortunate. These are handled under the SAE reporting system. A planned hospitalisation for pre-existing condition, or a procedure required by the protocol, without a serious deterioration in health, is not considered to be a serious adverse event.

Device deficiency

Inadequacy of a medical device related to its identity, quality, durability, reliability, safety or performance, such as malfunction, misuse or use error and inadequate labelling [ISO 14155: 3.15].

Health hazards that require measures

Findings in the trial that may affect the safety of study participants and, which require preventive or corrective measures intended to protect the health and safety of study participants SAE [ClinO Art. 37].

Causal Relationship of SAE [MEDDEV 2.7/3 revision 3, May 2015].

A causal relationship towards the medical device or study procedure should be rated as follows:

- **Not related:** The relationship to the device or procedures can be excluded.
- **Unlikely:** The relationship with the use of the device seems not relevant and/or the event can be reasonably explained by another cause, but additional information may be obtained.

- **Possible:** The relationship with the use of the investigational device is weak but cannot be ruled out completely. Alternative causes are also possible.

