12.1.1 Case Report Forms

Participant identities are coded using a participant identification number.

The PI will enter protocol defined data into a web based Electronic Case Report Forms using an EDC-software that conforms to 21 CFR Part 11 (FDA guidance) requirements. Site staff will be given access to the EDC system after a training. The data are checked automatically for plausibility and discrepancies. The generated appropriate error messages, allow the data to be confirmed or corrected before being saved in the database. At the end of the study, the PI must certify that the data entered into the Electronic Case Report Forms are complete and accurate. After database lock, the PI will receive a CD-ROM of the patient data for archiving at the site.

The CRF contains the following information:

Field	Author
Date of examination	PI
Subject birth year	PI
Participant identification number	PI
Age	PI
Sex	PI
Otoscopy	PI
Standard audiometry	PI
Hearing loss classification	PI
Eligibility	PI
Trial information provided	PI
Date of Informed Consent	PI
Inclusion / Exclusion Criteria	PI
Ear disease	PI
Control hearing device serial numbers	PI
Real ear measure	PI
Investigational device serial numbers	PI
Results from WaKo	PI
Questionnaires received	PI
Questionnaires returned	PI

Devices returned	PI
IFU received	PI
Results from preference questionnaire	PI
Results from product questionnaire	PI
Results from SSQ questionnaire	PI
AEs / SAEs, ADE / SADE	PI
Next appointment	PI
Name, date, signature of PI	PI

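### The adverse event table in 11.4.5 counts events by IMD style and severity only, so it cannot separate IMD-related events from RMD or background events, nor show how many people were affected

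*Protocol*

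**What the plan says.** Section 11.4.5 of the protocol describes the adverse event summary in one sentence: "Numbers of adverse events and serious adverse events will be cross-tabulated for each IMD style and categorised by severity". It then adds "No formal statistical analysis will be conducted, but AEs and SAEs will be closely monitored throughout the process". The dimensions given are AE or SAE, IMD style and severity, and the unit is the event.

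Other sections determine what goes into that table:

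- **What is solicited.** In 9.2.3.1 participants are told that "adverse events are not restricted to problems related to the hearing aids or their hearing"; the examples given include allergies and broken legs.
- **Which device.** The AE definition in 10.1.1 states "This includes events related to the IMD or the RMD and to the procedures involved". Under 6.2.1, everyone wears the RMD in the first field period and the IMD in the second.
- **What is recorded.** Section 10.1, which covers device deficiencies and all AEs including SAEs, says "Documentation includes dates of event, treatment, resolution, assessment of seriousness and causal relationship to device and/or study procedure". The CRF list in 12.1.1 has the entry "AEs / SAEs, ADE / SADE". Section 10.1.1 gives a five-level causality scale, under a heading that names SAEs.
- **Denominators.** Section 6.1 gives minimum sizes of 22, 22 and 11 for the three phases and allows phase 1 participants to join phase 2. Section 11.5 says the number of subjects in each analysis will be reported.

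**The concern.** The safety objective in 4.4 is to find unexpected behaviour of the IMD and new risk factors before release. For that purpose an adverse event table should let the reader see which events are attributed to the IMD and how many people had them. The table in 11.4.5 does neither, although the protocol collects what is needed for both.

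Two things are lost. First, attribution: a broken leg, discomfort from the RMD and discomfort from the IMD can all be entered under the same IMD style, distinguished only by severity. Second, the unit: three reports from one person and one report from each of three people give the same entry. At stake is how the study's own safety summary can be interpreted. Sample size, power and alpha are not affected.

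**Working it through.** **1. The plan's own figures.** Section 11.4.5 states no number. The relevant figures are the phase sizes. They add up as section 6.1 says: 22 + 22 + 11 = 55 people with no overlap, and 22 + 11 = 33 if phase 2 reuses all of phase 1. They also agree with section 11.2. The pilot effect size is 1.54/1.63 = 0.945 (stated 0.94). For a paired t-test at one-sided 2.5%, with a noncentral t distribution on n − 1 degrees of freedom and noncentrality d√n:

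| n | d | Power computed | Power stated |
|---|---|---|---|
| 11 | 0.94 | 80.2% | 80% |
| 22 | 0.65 | 82.8% | 83% |

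**2. What the table uses against what is collected.**

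| Item | Collected or defined in | Used in 11.4.5 |
|---|---|---|
| AE / SAE | 10.1, 12.1.1 | yes |
| Severity | 10.1 | yes |
| IMD style (phase) | by design | yes |
| Causal relationship to device or procedure | 10.1 | no |
| ADE / SADE | 10.1.1, 12.1.1 | no |
| Device worn at onset | event dates (10.1) and the switch at visit 2 (9.3) | no |
| Participants affected | derivable from the event records | no |

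The choice of events as the unit is not just loose wording. Section 11.4.6, the next one, asks for counts and percentages of people with protocol deviations, so the protocol makes the distinction when it intends to.

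**3. What one entry can mean.** Suppose a style shows 3 events (an assumed count). The proportion affected is x/N, with exact (Clopper-Pearson) 95% limits:

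| Situation | x/N | Proportion | 95% CI |
|---|---|---|---|
| 3 people, phase 1 or 2 | 3/22 | 13.6% | 2.9% to 34.9% |
| 3 people, phase 3 | 3/11 | 27.3% | 6.0% to 61.0% |
| 1 person, phase 1 or 2 | 1/22 | 4.5% | 0.1% to 22.8% |
| 1 person, phase 3 | 1/11 | 9.1% | 0.2% to 41.3% |

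The planned table shows 3 in every row. Knowing the number analysed distinguishes 22 from 11, but not three people from one. In each row the 3 events may also be background, RMD-related, IMD-related or a mixture.

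**4. Comparing styles.** At the same event rate per person, the expected count in phase 3 is 11/22 = 0.5 of that in phase 1 or 2. Raw counts across styles therefore have to be read against the number exposed.

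**The case against.** The strongest reply is that this is detail for the statistical plan, which is listed as an appendix and is not shown. Section 11.4.5 names one cross-tabulation; it neither rules out others nor contradicts another section. That limits the point: it cannot be said that no relatedness or participant-level summary exists. It does not remove it, because 11.4.5 is not silent. It fixes the unit and the dimensions, and they do not suit the data it will summarise.

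Several further objections stand, and they rule out stronger readings.

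- A reader might infer that there will be no denominator and that the Super Power style will therefore look safer. Section 11.5 promises the number of subjects in each analysis, and the phase sizes are stated. The halved count applies only to raw numbers read without that.
- A reader might infer that device harm would go undetected. Sections 5.3 and 9.2.3 place the device-specific safety questions in the product questionnaire, completed separately for the RMD and the IMD. Section 10.1.2 has the sponsor assess every SAE for causality, and related SAEs go to the authorities. With 33 to 55 people, case-level review is feasible.
- A reader might try to quantify how much of the table is uninformative. The protocol gives no share of events expected to be device-related, so any such figure would be an assumption.
- With no participants affected, the one-sided 95% upper limit, 1 − 0.05^(1/n), is 12.7% for n = 22 and 23.8% for n = 11. These limits depend on n alone and are no measure of the defect. If a style has zero AEs of any kind, the planned table already shows that nobody had an ADE.

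**Conclusion.** The point holds for the table as specified. It cannot separate IMD-related events from RMD or background events, and it cannot distinguish repeat events in one person from events in several. With 3 events, the share of participants affected could be anywhere from 4.5% to 27.3%, depending on phase and on whether the events recur in one person; the count of 3 is illustrative.

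The conclusion assumes that 11.4.5 is followed as written and that the unseen statistical plan does not already add these breakdowns. It also reads the phrase about each IMD style as covering the whole phase, including the RMD period. If the sponsor means IMD-period events only, the section should say so; pooling with background events and counting events rather than people would remain.

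It is a reporting weakness that should be corrected. It does not show that the study lacks safety assessment or that one style would be misrepresented as safer.

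**What to change.** Amend 11.4.5 so that the adverse event table reports, per phase (style) and per device worn at onset (RMD or IMD):

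- the number and percentage of participants with at least one event, together with the event count;
- each broken down by severity, by related or not related to device or procedure, and by ADE/SADE.

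Four details need stating:

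- **Denominator.** Use the number actually exposed to each device, not a fixed 22, 22 and 11. Section 6.1 gives these as minimum sizes, section 7.4 allows replacements, and someone who withdraws before visit 2 has worn only the RMD.
- **Causality scale.** Apply the five levels of 10.1.1 to SAEs, where the protocol places them. For other AEs a related/not related split is enough, based on 10.1 and the ADE field.
- **Overall row.** Count each person once, since phases 1 and 2 may share participants.
- **Clinic days.** Both devices are worn at visits 2 and 3, so say how an event starting on those days is assigned.

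The cost is a sentence or two of protocol text and a few extra table rows from data already collected. Sample size and alpha do not change.
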